### **8.3.5      Suicidal Ideation and Behavior Risk Monitoring (Columbia-Suicide Severity Rating Scale)**

GNX is considered to be a CNS-active intervention. GNX is related to products with an increased risk of suicidal ideation or behavior. Participants with TSC may occasionally develop suicidal ideation or behavior.

Participants being treated with GNX should be monitored appropriately and observed closely for suicidal ideation and behavior (SIB) or any other unusual changes in behavior, especially at the beginning and end of the course of intervention, or at the time of dose changes, either increases or decreases. Participants who experience signs of SIB should undergo a risk assessment. All factors contributing to SIB should be evaluated and consideration should be given to discontinuation of the study intervention.

When informed consent or assent has been given, participants or parents/caregivers of participants being treated with GNX should be alerted about the need to monitor participants for the emergence of unusual changes in behavior, as well as the emergence of suicidal ideation and behavior and to report such symptoms immediately to the study investigator.

The C-SSRS will be used to rate the participant's degree of suicidal ideation on a scale ranging from "no suicidal ideation" to "active suicidal ideation with specific plan and intent" (Posner et al, 2011) (Section 10.11). The C-SSRS will be assessed in all participants  $\geq$  11 years of age, if appropriate, otherwise, clinical judgment will be used.

If the participant has a positive result for C-SSRS, the medical monitor should be contacted within 24 hours and the medical monitor will determine if the individual should discontinue the trial.

The C-SSRS will be completed at Visit 1 (First Visit of the OLE) (and compared with data collected in the parent study), and then 6-monthly at Visit 3 (Week 26), Visit 5 (Week 52), Visit 7 (Week 78), Visit 9 (Week 104), Visit 11 (Week 130), Visit 13 (Week 156), and Visit 14 (Week 160) (and compared with data collected in the previous visit).

### **8.3.6      Concomitant Anti-seizure Medicine Levels**

If the levels of ASM co-administered with the IP are measured routinely, this information will be recorded in the eCRF during the study.

Further details are provided in the SOA (Table 1).

### **8.3.7      Investigational Product Pharmacokinetics**

Please refer to Section 8.6 for additional details regarding PK assessments.

The results, date, and time of last ASM dose will be recorded in the eCRF.

### **8.3.8      Pregnancy Testing**

A serum pregnancy test is required for all WOCBP at Visit 1 on Day 1 of this OLE study. Urine pregnancy testing will then be performed every 4 weeks throughout the OLE using take-home pregnancy tests. Any positive home pregnancy test will be followed up with a confirmatory serum pregnancy test.

## **8.4      Adverse Events and Serious Adverse Events**

The definitions of unsolicited and solicited AEs and SAEs can be found in Section 10.4.

AEs will be reported by the participant (or, when appropriate, by parent/caregiver/LAR) throughout the study (Table 1).

The investigator and any qualified designees are responsible for detecting, documenting, and recording events that meet the definition of an AE or SAE and remain responsible for following up all AEs OR AEs that are serious, considered related to the study, or that caused the participant to discontinue the IP and the study (Section 7).

The reference for safety information for this study is the GNX IB, which the sponsor has provided under separate cover to all investigators. For additional details, please consult the most current IB.

The method of recording, evaluating, and assessing causality of AEs and SAEs and the procedures for completing and transmitting SAE reports are provided in Section 10.4.

All initial and follow-up SAE reports must be reported by the investigator to Marinus' drug safety vendor within 24 hours of the first awareness of the event. Note: The 24-hour reporting requirement for SAEs does not apply to reports of abuse, misuse, overdose, or medication errors unless they result in an SAE.

The investigator must complete, sign, and date the Marinus Clinical Study Serious Adverse Event Form and verify the accuracy of the information recorded on the form with the corresponding source documents (Note: Source documents are not to be sent unless requested) and fax or e mail the form to Marinus' drug safety vendor or its delegate.

### **8.4.1      Time Period and Frequency for Collecting Adverse Event and Serious Adverse Event Information**

All AEs are collected from the time of the first dose of the IP in the OLE until the defined follow-up period at the timepoints specified in the SOA (Section 1.3). Any AE that begins in a parent study and is ongoing at the time of the first dose of IP in the OLE will be included as an AE in the OLE. This includes events occurring during the initial visit in the study, regardless of whether or not the IP has been administered. All AEs reported after the initiation of IP will be considered treatment-emergent AEs. Where possible, a diagnosis rather than a list of symptoms should be recorded. If a diagnosis has not been made, then each symptom should be listed

individually. All AEs should be captured on the appropriate AE pages in the eCRF and in source documents. In addition to untoward AEs, unexpected benefits outside the IP indication should also be captured on the AE eCRF page.

Medical occurrences that begin before the start of study intervention but after obtaining informed consent will be recorded as medical history/current medical conditions, not as AEs.

All AEs must be followed to closure (the participant's health has returned to baseline status or all variables have returned to normal), regardless of whether the participant is still participating in the study. Closure indicates that an outcome is reached, stabilization is achieved (the investigator does not expect any further improvement or worsening of the event), or the event is otherwise explained. When appropriate, medical tests and examinations are performed so that resolution of event(s) can be documented.

All SAEs (regardless of relationship to study) are collected from the time the participant/parent(s)/LAR(s) signs the informed consent/assent until the defined follow-up period stated and must be reported to Marinus' drug safety vendor within 24 hours of the first awareness of the event.

In addition, any SAE considered "related" to the IP and discovered by the investigator at any interval after the study has completed must be reported to Marinus' drug safety vendor within 24 hours of the first awareness of the event.

Investigators are not obligated to actively seek information on AEs or SAEs after conclusion of the study participation. However, if the investigator learns of any SAE, including a death, at any time after a participant has been discharged from the study, and he/she considers the event to be reasonably related to the study intervention or study participation, the investigator must promptly notify the sponsor.

#### **8.4.2      Method of Detecting Adverse Events and Serious Adverse Events**

The method of recording, evaluating, and assessing causality of AEs and SAEs and the procedures for completing and transmitting SAE reports are provided in Section 10.4.

Care will be taken not to introduce bias when detecting AEs and/or SAEs. Open-ended and nonleading verbal questioning of the participant is the preferred method to inquire about AE occurrences.

#### **8.4.3      Follow-up of Adverse Events and Serious Adverse Events**

After the initial AE/SAE report, the investigator is required to proactively follow each participant at subsequent visits/contacts. All SAEs (and non-serious AEs of special interest (as defined in Section 8.4.8) will be followed until resolution, stabilization, the event is otherwise explained, or the participant is lost to follow-up (as defined in Section 7.3). Further information on follow-up procedures is provided in Section 10.4.

#### **8.4.4 Regulatory Reporting Requirements for Serious Adverse Events**

Prompt notification by the investigator to the sponsor of an SAE is essential so that legal obligations and ethical responsibilities towards the safety of participants and the safety of a study intervention under clinical investigation are met.

The sponsor has a legal responsibility to notify both the local regulatory authority and other regulatory agencies about the safety of a study intervention under clinical investigation. The sponsor will comply with country-specific regulatory requirements relating to safety reporting to the regulatory authority, Institutional Review Board/Independent Ethics Committee (IRB/IEC), and investigators.

Investigator safety reports must be prepared for suspected unexpected serious adverse reactions (SUSARs) according to local regulatory requirements and sponsor policy and forwarded to investigators as necessary.

An investigator who receives an investigator safety report describing an SAE or other specific safety information (eg, summary or listing of SAEs) from the sponsor will review and then file it along with the IB and will notify the IRB/IEC, if appropriate according to local requirements.

##### **8.4.4.1 Suspected Unexpected Serious Adverse Reaction**

A SUSAR is defined as an SAE that meets both the following criteria with respect to IP:

Suspected — is assessed as related to IP

Unexpected — compared to the IP-related AEs described in the IB, Reference Safety Information, the event meets any of the following criteria:

- The event has not been previously described.
- The event is now characterized as more severe.
- The event is now characterized more specifically (eg, an event of “interstitial nephritis” in a participant receiving an agent previously described as associated with “acute renal failure”).

In clinical trials involving ill participants, events considered related to the natural history of the disease under study or to lack of efficacy (that is, the event is considered more likely related to those factors than to other factors, including study drug) are not considered “unexpected”.

##### **Requirements for Expedited and Periodic Reporting of Adverse Events:**

SUSARs are required to be reported rapidly to regulatory authorities and to IRBs/IECs (within 7 days of initial notification for fatal or life-threatening SUSARs, within 15 days for all other SUSARs). Therefore, as with all SAEs, the site must report the event to Marinus’ drug safety vendor within 24 hours of being made aware of the event. The Sponsor and the Investigator will work together to meet these reporting requirements.

#### **8.4.5 Clinical Laboratory and Other Safety Evaluations**

A change in vital signs, physical, neurological, and developmental examinations, 12-lead ECG parameters, or clinical laboratory values can represent an AE if the change is clinically significant or if, during treatment with the IP, a shift of a parameter is observed from a normal value to an abnormal value, or there is a further worsening of an already abnormal value. When evaluating such changes, the extent of deviation from the reference range, the duration until return to the reference range (either while continuing treatment or after the end of treatment with the IP), and the range of variation of the respective parameter within its reference range must be taken into consideration.

If, at the treatment period, there are abnormal vital signs, physical, neurological, and developmental, 12-lead ECG, or clinical laboratory values that were not present in the pretreatment findings observed closest to the start of study treatment, further investigations should be performed until the values return to within the reference range or until a plausible explanation (eg, concomitant disease) is found for the abnormal values.

The investigator should decide, based on the above criteria and the clinical condition of a participant, whether the change is clinically significant and therefore, represents an AE.

#### **8.4.6 Death Events**

Any SAE that results in the participant's death (ie, the SAE was noted as the primary cause of death) must have fatal checked as an outcome, with the date of death recorded as the resolution date. For all other events ongoing at the time of death that did not contribute to the participant's death, the outcome should be considered not resolved, without a resolution date recorded.

For any SAE that results in the participant's death or any ongoing events at the time of death, unless another IP action was previously taken (eg, the drug was interrupted, reduced, or withdrawn), the action taken with the IP should be recorded as "dose not changed" or "not applicable" (if the participant never received the IP). The IP action of "withdrawn" should not be selected solely as a result of the participant's death.

#### **8.4.7 Disease-related Events and/or Disease-related Outcomes Not Qualifying as Adverse Events or Serious Adverse Events**

Symptoms of the disease under study should not be classified as AEs as long as they are within the normal day-to-day fluctuation or expected progression of the disease. This includes seizures typical for that participant unless the seizures are changed in character, frequency, or duration. Significant worsening of the symptoms should be recorded as an AE.

The following disease-related events are common in participants with epilepsy and can be serious/life-threatening:

- Seizures.
- SE.

- Falls/trauma/accidents.

As these events are typically associated with the disease under study, they will not be reported according to the standard process for expedited reporting of SAEs even though the event may meet the definition of an SAE. These events will be recorded within 5 business days of when they are reported to the site. These disease-related events will be monitored on a routine basis.

Note: However, if either of the following applies, then the event must be recorded and reported as an AE/SAE (instead of a disease-related event):

- The event is, in the investigator's opinion, of greater intensity, frequency, or duration than expected for the individual participant, or
- The investigator considers that there is a reasonable possibility that the event was related to study intervention.

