### **2.3.1 Risk Assessment**

CNS-related effects (such as somnolence, sedation, and gait disturbance) have been identified as an important risk related to the mechanism of action of GNX. In placebo-controlled studies, the most common CNS effects were somnolence, dizziness, fatigue, sedation, and gait disturbance. Of the AEs present at frequency > 1% and 2 times the frequency of placebo in the aggregate AE data, all 12 AEs are related to CNS function. The most common CNS-related AEs that led to discontinuation reported in placebo-controlled studies were dizziness (GNX 1.1%; placebo 0.4%); somnolence (GNX 0.9%; placebo 0.4%); and fatigue (GNX 0.8%; placebo 0.1%). These CNS effects were typically non-serious, mild to moderate in severity, and did not lead to discontinuation of treatment. However, in Study 1042-SE-2001, 2 SAEs of sedation were reported and led to early discontinuation and revision of the reference safety information.

The safety assessments to be performed in this study include vital signs, physical, neurological, and developmental examinations, 12-lead electrocardiogram (ECG), clinical laboratory tests, AE assessments, and Columbia Suicide Severity Rating Scale (C-SSRS). These are standard evaluations to ensure participant safety in this clinical study.

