### 4.3. Statistical Methods for Primary Safety Analyses

#### 4.3.1. Adverse Events

Adverse events (AEs) are collected from the time of informed consent/assent through the defined follow-up period. AEs are coded using MedDRA dictionary, version 24.0 and are

categorized by system organ class (SOC) and preferred term (PT). A treatment-emergent AE (TEAE) is defined as an AE that starts or worsens on or after the first day of dosing with IP. Detailed by-patient listings of all AEs reported during the study will be provided and will include verbatim and coded terms for each AE.

For the safety Analysis Set, the following tabular summaries will be created:

- An overall summary of TEAEs will present the number and percentage of subjects with at least 1 reported TEAE, study drug related TEAE, serious TEAE, TEAE of Grade 3 or higher, study drug infusion interruption, and death
- TEAEs by system organ class and preferred term
- TEAEs by system organ class, preferred term, and maximum severity
- Study drug related TEAEs by system organ class and preferred term
- TEAEs by decreasing frequency of preferred term
- Moderate or severe TEAEs by system organ class and preferred term
- Moderate or severe study drug related TEAEs by system organ class and preferred term
- TEAEs that led to study drug infusion interruption by system organ class and preferred term
- Serious TEAEs by system organ class and preferred term
- Serious study drug related TEAEs by system organ class and preferred term

For incidence reporting, if a subject reported more than 1 AE that was coded to the same preferred term/system organ class, the subject will be counted only once for that specific preferred term/system organ class. For TEAEs presented by severity, the worst severity for each event during the clinical trial will be presented for each subject. If the severity is missing for a TEAE, then a severity of “Severe” will be assigned. The imputed values for severity assessment will be used for incidence summaries, while the actual values will be used in data listings.

For TEAEs presented by relationship to study drug, the closest relationship to study drug for each event during the clinical trial will be presented for each subject. If the relationship to investigational product is missing for a TEAE, a causality of “Related” will be assigned. The imputed values for relationship assessment will be used for incidence summaries, while the actual values will be presented in data listings.

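### Serious seizures, status epilepticus and falls judged typical and unrelated can be absent from the primary AE/SAE tables: Protocol 8.4.7 conflicts with 8.4.1, and the SAP gives disease-related events no safety output

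*Protocol*

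**What the plan says.** Protocol 8.4.7 is headed "Disease-related Events and/or Disease-related Outcomes Not Qualifying as Adverse Events or Serious Adverse Events". It introduces seizures, SE and falls, trauma or accidents with the words "The following disease-related events are common in participants with epilepsy and can be serious/life-threatening", and says that they are to "not be reported according to the standard process for expedited reporting of SAEs even though the event may meet the definition of an SAE". In place of that process, "These events will be recorded within 5 business days of when they are reported to the site", with routine monitoring. No form or dataset is named.

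The section then sets two conditions, either of which is enough to bring an event back: the investigator finds it stronger, more frequent or longer than expected for that person, or sees a reasonable possibility that treatment caused it. If one is met, "then the event must be recorded and reported as an AE/SAE (instead of a disease-related event".

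Protocol 8.4.1 states: "All SAEs (regardless of relationship to study) are collected" from consent onward, with a 24-hour reporting requirement. It makes no reference to 8.4.7.

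The primary endpoints (Protocol 3, SAP 2.3.1) begin with the incidence and severity of AEs and SAEs. SAP 4.3.1 builds every safety table from TEAEs, for example "Serious TEAEs by system organ class and preferred term". Its listings cover AEs, SAEs, TEAEs leading to drug interruption and fatal SAEs. The SAP text does not mention disease-related events.

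**The concern.** This is an uncontrolled, open-label study whose primary result is a description of AEs and SAEs. With no comparator to absorb misclassification, any rule that decides which events become AE/SAE records shapes the primary result directly.

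The events set aside matter for this drug. Protocol 2.2.2.2 puts seizure and SE first in its list of the most frequent SAEs across completed ganaxolone studies. Protocol 2.3.1 says that "CNS-related effects (such as somnolence, sedation, and gait disturbance) have been identified as an important risk", and falls are a plausible consequence of sedation or gait disturbance.

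Two things are at stake. First, the serious-event rate could be understated. Second, one site following 8.4.1 and another following 8.4.7 could classify the same event differently, which would make the SAE count hard to interpret even if few events are involved.

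**Working it through.** **Step 1: can an event meet the SAE definition and still not be an SAE record?** The sentence in 8.4.7 that waives expedited reporting does not settle this, because it concerns only the route and speed of reporting. Two other parts of the section do. The heading says that these events do not qualify as AEs or SAEs. The exception says that a qualifying event is reported as an AE/SAE instead of as a disease-related event, so the two categories exclude each other. A serious SE episode or fall judged both typical for the participant and unrelated therefore stays outside the AE/SAE records.

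**Step 2: does 8.4.1 close the gap?** Under 8.4.1 the same event would be collected and reported within 24 hours. Under 8.4.7 it is recorded within 5 business days outside that process. Neither section says which prevails. Protocol 8.4 repeats the 24-hour rule without exception, and Protocol 10.4.2 names convulsions as an example of an event usually considered serious.

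**Step 3: does the SAP pick the events up elsewhere?** A TEAE must first be an AE (SAP 4.3.1), so an event outside the AE records cannot enter any TEAE table. Countable seizures are summarised as efficacy: 28-day frequency (SAP 4.4.1), responders (4.4.2) and seizure-free days (4.4.5). These are Year 1 endpoints and carry no seriousness; the eDiary also runs for the first year only (Protocol 4.1), out of about three. SE and falls have no safety output of their own outside AE/SAE records.

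**Step 4: illustrative size.** The documents give no figure for the share of serious events that would be set aside, so there is no plan figure for this quantity to reproduce. The only anchor is the pooled SAE rate in Protocol 2.2.2.2:

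- p = 118/2172 = 5.43%, which agrees with the stated 5.4%.
- Expected participants with an SAE = N × p. With N = 169 (Protocol 9.4) this is 9.18; with N = 150 (SAP 3.1) it is 8.15.
- Let f be the assumed share of those participants whose serious events are all classed as disease-related. Missing = N × p × f. Rate shown = p × (1 − f). Chance that at least one participant is missing = 1 − (1 − p × f)^N.

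| f (assumed) | Rate shown | Missing, N = 169 | Chance of at least one | Missing, N = 150 | Chance of at least one |
|---|---|---|---|---|---|
| 10% | 4.89% | 0.92 | 60.2% | 0.81 | 55.8% |
| 25% | 4.07% | 2.30 | 90.1% | 2.04 | 87.1% |
| 50% | 2.72% | 4.59 | 99.0% | 4.07 | 98.4% |

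The pooled rate mixes studies of differing duration, so it is a rough anchor for an extension of up to three years.

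**The case against.** The strongest reply is that the events most likely to signal harm are routed back. Protocol 8.4.7 makes significant worsening an AE, as well as seizures that change in character, frequency or duration. Protocol 10.4.1 does the same for exacerbation of an existing condition, and for the sequelae of lack of efficacy where they meet the AE or SAE definition. A fall that the investigator attributes to sedation meets the relatedness condition. Somnolence, sedation and gait disturbance are not on the 8.4.7 list, so they remain ordinary AEs. All of this stands, and it narrows the gap to serious events judged both typical and unrelated. It does not close the gap: without a control arm, those two individual judgements decide what reaches the primary endpoint.

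Three stronger readings are tempting, and the documents do not support them:

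- A reader might infer that all seizures, SE and falls are kept out of safety reporting. The two return conditions rule that out.
- A reader might infer that the SAP never tabulates these events. Countable seizures do appear in the Year 1 efficacy summaries, and CGI-CSID covers seizure intensity and duration to Week 156. The table shells are a separate document (SAP 8) and could hold more. The supportable statement is that the SAP text calls for no safety table or listing of disease-related events.
- A reader might assume that 5% to 20% of participants have such a serious event and that half are set aside, which gives 4 to 17 of 169. Neither input is in the documents, and 20% is almost four times the pooled all-cause SAE rate.

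**Conclusion.** The point holds in its limited form. Followed as written, the plan could leave serious seizures, SE and falls that are judged typical and unrelated out of the AE/SAE tables that form the primary result, and no other planned safety output would show them. The conflict between Protocol 8.4.1 and 8.4.7 is plain on the text and rests on no assumption.

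The size is unknown. The illustration of about 1 to 5 missing participants rests on three assumptions: that the pooled 5.4% applies here, that f lies between 10% and 50%, and that participants are independent for the probability column. It shows that the effect could be noticeable against about 9 expected participants with an SAE; it is not an estimate. The difference between the planned N of 169 and 150 barely changes it. This should be corrected, but it does not undermine the study's design.

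**What to change.** 1. Reconcile Protocol 8.4.7 with 8.4.1 (and with the general 24-hour rule in 8.4), so that every site handles a serious seizure, SE episode or fall in the same way.
2. State where disease-related events are recorded, and confirm that seriousness is captured. The CRF version that the SAP cites is not part of the reviewed documents, so this cannot be assumed.
3. In SAP 4.3.1, add a count and a listing of disease-related events by type (seizure; SE; fall, trauma or accident) and by seriousness.
4. Add one combined summary of participants with a serious TEAE or a disease-related event meeting SAE criteria, counting each participant once. This summary does not depend on which of the two categories a site chose. Rates per patient-year are optional.

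The cost is a few extra outputs, a possibly higher reported serious-event rate, and a small CRF change if seriousness is not already collected. The SAP part can be made by SAP amendment before database lock, as SAP 6 provides.
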